Appendix Q- Supplement: Reach Out Cognition

[figure not shown]
Introduction and Background

We propose Reach Out Cognition which will extend Reach Out data collection past the current 12 months to 15 and 18 months. During Reach Out Cognition, we aim to assess novel approaches to mobile health (mHealth) self-administered cognition and blood pressure (BP) measurements. These approaches may include cognitive assessments via mobile applications (apps) and Web-based surveys, and wireless BP measurements via Bluetooth-enabled blood pressure cuffs and apps. The launch date is pending approval of a supplement and/or amendment and participant completion of the parent study 12-month outcome assessment (we anticipate July 2020).

Design

Recruitment:

The study population for Reach Out Cognition will be drawn from Reach Out participants who complete the Reach Out intervention and are defined as: participants who complete the 12-month outcome assessment. We anticipate about 240 participants will have completed Reach Out's 12-month outcome assessment and will be eligible for Reach Out Cognition. At the time of the final (12-month) outcome assessment, participants will be introduced to the opportunity of continuing for another ~6 months with the added mHealth measures.

Inclusion:

Participants of the Reach Out protocol that are no more than 6 months after completion of their 12-month outcomes are eligible. A subset of Reach Out participants will not have smartphones. However, our goal is inclusivity and generalizability and will allow for inclusion of all cell phones with the capability to send picture text-messages. Thus we designed Reach Out Cognition with the capability to include these participants, albeit outcome assessments procedures will differ.

Exclusion:

Participants who have withdrawn or not completed follow up visits.

Screening:

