Prior to consent, participants may be screened for baseline cognition via the mini-Montreal Cognitive Assessment (MoCA) or similar. This would be preceded by verbal screening consent ([Appendix V](#)). Participants may either be given a feedback sheet in person, via postal mail, or text message to link regarding their MoCA score if fully completed ([Appendix S](#)). If score <11, or similar test specific cognitive threshold, we will state the MoCA suggested response to this range, and participant will not be consented for the study. It will be suggested that participant may wish to share the MOCA score with their doctor to discuss memory and thinking. Participant's doctor will be able to answer questions and decide whether more testing or treatments are right. These tests are not diagnostic.

Consent:

If 12-month outcome is in-person, and the participant agrees to continued participation, an informed consent will be signed (may be electronic and built into redcap as previous informed consent) by the participant before any study procedure is done.

However, in the time of COVID-19, the consent process and subsequent surveys may also be done virtually, if performing a 12-month outcome via tele-outcome per Reach Out protocol. In this circumstance, we would perform remote recruitment and consent. The research staff will follow a phone consent script ([Appendix R](#)), this may be done with whatever means best possible for participant (telephone, video, etc). The research staff will ask for the last name, and month and year of birth as confirmation that we are speaking to expected patient. Only once confirmed, will the research staff begin the process of consent. The consent process will be performed by the research staff in a private environment to provide the most privacy possible. The research staff will explain the study to participants during the consenting process. Interested participants will be enrolled in the study after providing verbal consent (for remote recruitment). The research staff will discuss questions with the participant, and research would only begin after informed consent is obtained.

For participants who are within 6 months of their 12 month visit but have completed their 12 month outcome visit prior to approval of this amendment, we may attempt to re-contact them to perform remote recruitment and consent.

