Reach Out will use a secure, password-protected web-based application, REDCap and/or qualtrics, for data collection and surveys. The text messages and picture messages are within a SSL encrypted web-based application with secure log-ins to access. The Bluetooth app is subject to the terms and conditions of the particular company, which will be presented to the participant. The data being utilized on these apps (blood pressures) will only be connected with personal information if the participant chooses to use their name and email in the profile description and sharing capability. Regardless, additional personal identifiable information will not be associated with the blood pressures or the app from Reach Out. Additionally, any data submitted by participants via direct download from BP app and sent to study team by email correspondence will be through a secure study team email. Only Reach Out study team members will have access to the study email account. All data submissions received on the study email account will

be transferred to the password-protected database. All Reach Out study team members will receive data security training.

Outcomes

We will measure acceptability, feasibility and satisfaction which are necessary for large scale use of mHealth BP and cognition measures. We will use these scales or similar validated measures of acceptability, feasibility and satisfaction.

Acceptability is the perception among participants that the mHealth assessments are achievable and agreeable. Acceptability will be assessed by the proportion of Reach Out 12-month outcome participants who continue into Reach Out Cognition.

Feasibility is the extent to which the mHealth assessments can be successfully carried out. Feasibility will be assessed by the proportion of participants who complete the mHealth cognitive assessment and the BP assessments separately. We will declare feasibility if greater than 50% of participants provide at least one cognitive measure.

Satisfaction is the perception that upon completion of the mHealth assessments participants found them agreeable. Satisfaction will be measured with a text survey to all participants. The satisfaction survey is 4-item, written at a 5th grade reading level and takes less than 5 minutes to complete. Responses are a 5 item likert scale. In addition, we may invite a subset of participants to participate in a focus group.

Focus Groups

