To assess participant satisfaction with mHealth self-administered cognitive and blood pressure measures, we may conduct up to 4 focus groups of about 10 participants each of Reach Out Cognition. We anticipate the focus group to last about 60 minutes and will be conducted at a location convenient to the participants or virtually via secure means provided by the University of Michigan (<https://safecomputing.umich.edu/dataguide/?q=home>). Focus groups will be based on a semi-structured interview guide. Given this is minimal risk, and conversational, this will not be submitted to the IRB. During the focus group team members will assist in taking structured notes. Participants will be given \$25 in appreciation of their time.

Analysis

Descriptive statistics will be used to evaluate acceptability, feasibility and satisfaction. The denominator is the number of Reach Out participants who complete the 12 month assessments. Regarding feasibility, we will separately determine the feasibility by mHealth measure (i.e. cognition vs. BP), phone type (i.e. smartphone vs. feature phone) and operating system type (iOS vs. Android vs. Windows) as a continuous and dichotomous (>50% completion of each assessment type) measure. The satisfaction scale will be assessed for all participants. Given the difference in procedures by phone type, we will compare satisfaction between the smartphone and feature phone users using a Kruskal-Wallis test.

Minorities and women: Per NIH policy, the primary outcomes will be analyzed for evidence of differential treatment effects in subgroups determined by sex/gender, race, and ethnicity.

Upon recruitment during the parent study final outcome visit, we may collect a Montreal Cognitive Assessment (MoCA). We anticipate that approximately 10-20% of our participants will have previously undiagnosed mild cognitive impairment. In addition, using the Neuro-QOL cognition battery, we will determine how much the Reach-Out Cognitive cohort differs from the expected values for the patient reported outcomes. Using existing data on trajectory of change in MoCA based on age, we will develop estimates of the likely cognitive status of ED patients with hypertension 12 months prior to enrollment in Reach Out Cognitive (i.e. at the time initially seen in ED and enrolled in the parent Reach Out trial).

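### Appendix Q measures acceptability over all 12-month completers, so completers whom the supplement turns away or never invites are scored the same as those who decline

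*Protocol*

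**What the plan says.** All of this is in Appendix Q of the protocol (Reach Out Cognition).

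- **Construct (Outcomes).** "Acceptability is the perception among participants that the mHealth assessments are achievable and agreeable".
- **Measure (Outcomes).** "Acceptability will be assessed by the proportion of Reach Out 12-month outcome participants who continue into Reach Out Cognition". The text mentions scales or similar validated measures in general terms, but this proportion is the only acceptability measure it specifies.
- **Denominator (Analysis).** Directly after a sentence naming acceptability, feasibility and satisfaction: "The denominator is the number of Reach Out participants who complete the 12 month assessments". Nobody is removed from it.
- **Time window (Inclusion).** "Participants of the Reach Out protocol that are no more than 6 months after completion of their 12-month outcomes are eligible".
- **Phone (Inclusion).** Feature phones are allowed, provided they can send picture messages.
- **Cognitive screen (Screening).** "Prior to consent, participants may be screened for baseline cognition via the mini-Montreal Cognitive Assessment (MoCA) or similar". For a score below 11, or below a similar threshold on another test, "participant will not be consented for the study".
- **Invitation (Recruitment, Consent).** Participants are told of the supplement at the 12-month assessment. For those who had that assessment before the amendment was approved, "we may attempt to re-contact them to perform remote recruitment and consent".
- **Exclusion.** "Participants who have withdrawn or not completed follow up visits".

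The Recruitment paragraph expects about 240 completers and describes them all as eligible.

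**The concern.** The construct is an opinion held by participants, and the measure is the share who continue. The two agree only if everyone in the denominator was free to continue and was asked. The supplement's own rules mean that this need not be so. A willing person who fails the pre-consent screen is turned away by the study, yet sits in the same cell as someone who was asked and said no. A person who was never re-contacted has expressed no view at all.

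The reported proportion therefore mixes willingness with eligibility rules and recruitment effort. It would shift with the launch date, with how often the screen is used and with how many earlier completers staff call, even if opinion of the assessments stayed the same. The appendix presents these outcomes as a basis for judging wider use, so a reader needs to be able to separate the two. The error can only go downwards.

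**Working it through.** **1. The plan's own figure.** No acceptability target or expected value is stated, so the only number to reproduce is the denominator. Protocol Section 9.3 and the SAP sample-size paragraph give 480 randomized and 50% loss: 480 × (1 − 0.50) = 240, which matches the 240 in Appendix Q. Section 9.3 later raises randomizations by 50%, to 480 × 1.5 = 720, but keeps the target of 240 completers (240/720 = 33%). The denominator is unchanged.

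**2. Can a 12-month completer be barred or missed?** Yes, by four routes.

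- *Screen failure.* The screen comes after the 12-month assessment and before consent.
- *Window.* A completer more than 6 months past the 12-month outcome falls outside the inclusion rule.
- *Phone.* Protocol Section 7.1.2 lets parent-trial participants use a mailed disposable camera or a friend's phone, and an in-person visit needs no photograph. A person can therefore complete month 12 without a picture-capable phone.
- *No invitation.* Re-contact of those who completed before the amendment is optional.

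**3. Formula.** Let N be the number of completers, x the share refused or not invited, and a the uptake among the rest.

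- Eligible and invited = N(1 − x); continuers = aN(1 − x).
- Reported acceptability = aN(1 − x)/N = a(1 − x).
- With the denominator limited to those eligible and invited, the result is aN(1 − x)/[N(1 − x)] = a.
- Relative understatement = [a − a(1 − x)]/a = x.

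**4. Numbers.** N = 240 is from the plan. The values of x and a are assumptions, because the documents give neither. Counts are rounded to whole people.

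| x | Eligible and invited | Ceiling (a = 100%) | Continuers if a = 80% | Reported |
|---|---|---|---|---|
| 0% | 240 | 100% | 192 | 80.0% |
| 10% | 216 | 90.0% | 173 | 72.1% |
| 20% | 192 | 80.0% | 154 | 64.2% |
| 30% | 168 | 70.0% | 134 | 55.8% |

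**5. What the documents say about x.** They give no rate for any of the four routes. There is some evidence that x may be small.

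- Dementia or cognitive impairment is already an exclusion of the parent trial, and use of the screen is optional.
- Section 3 dates the intervention from March 2019, which puts 12-month outcomes at about March 2020. The February 2020 newsletter says these outcomes are just beginning. The supplement's anticipated launch is July 2020, four to five months later and inside the 6-month window. A later launch would put more people outside it.
- Routine invitation takes place at the 12-month assessment, so only people who completed before the amendment could go uninvited.

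**The case against.** The best defence is that the denominator is stated openly in two places and is a legitimate choice. Continuation among all completers is transparent and conservative, and it cannot be raised by inviting selectively. The definition includes whether the assessments are achievable, and lacking a suitable phone arguably bears on that. Acceptability is summarized descriptively, with no threshold or test; the 50% rule in the appendix belongs to feasibility.

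Much of this stands. It is a good reason to keep the all-completer proportion, but as a measure of reach. It does not turn a screen failure or an uninvited person into evidence about perception, which is the construct the appendix names.

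Three stronger readings are tempting, and the documents do not support them.

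- *That 10 to 20% will fail the screen, capping acceptability at 80 to 90% before any other loss.* The 10 to 20% in the Analysis paragraph is the expected rate of previously undiagnosed mild cognitive impairment. It is not the rate of scores below 11 on the short screen. The feedback form in Appendix S uses a different cut, below 26 of 30. A failure rate near zero is compatible with the text.
- *That the exclusion removes 12-month completers who missed the 6-month visit.* The wording taken alone allows this, but the Recruitment paragraph of the same appendix defines the population by the 12-month assessment. Read together, the exclusion describes people outside that population. At most it needs clarifying.
- *That a known group was never invited.* Re-contact is permitted but not required, so such a group is possible, not certain.

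**Conclusion.** The mismatch between construct and measure is real and in the current text. Followed as written, the plan scores completers whom the supplement refused or did not ask as non-acceptors, and understates willingness by a relative amount equal to x. The size is unknown. Under the assumed 0 to 30%, a true 80% uptake would be reported as 80% down to 56%, and the lower end has no support beyond the assumption. Nothing in the parent trial's primary or secondary analyses depends on this figure, and no decision rule is attached to it. It is a minor point, worth making because the remedy is specific and cheap.

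**What to change.** 1. In the Outcomes paragraph of Appendix Q, define acceptability as those who consent divided by 12-month completers who were eligible for the supplement and invited. State that a person who refuses the screen itself has declined and stays in the denominator.
2. Amend the denominator sentence in the Analysis paragraph to match, for acceptability specifically. Otherwise it would contradict the new definition.
3. Keep continuers over all 12-month completers as a separate, labelled reach figure.
4. Record, and show in the flow from all 12-month completers, the numbers who failed the screen, were out of window, had an unsuitable phone, were not contacted, or declined.
5. Optionally, reword the exclusion so that it refers to the 12-month assessment, in line with the population definition.

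The cost is a few sentences, a second proportion in the report, and a short tally kept during recruitment. The tally has to be set up: the screening log in protocol Section 5.3.1 covers recruitment to the parent trial, and the documents describe none for the supplement.

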Appendix S- Supplement: Feedback forms

1.0 3.11.2020

Reach Out Cognition
Cognitive Screening
Date:

We did a cognitive test today as a part of the Reach Out Cognition Project. Your score on the Montreal Cognitive Assessment (MoCA test) was: _____ out of 30.

What does your cognitive test score mean?

If your score was	Comment and Action
26 or above	Your Montreal Cognitive Assessment (MoCA test) score today is within the normal range . You don't need to do anything right now.
Less than 26	Some people with scores in this range have normal memory and thinking, and others have had changes in their memory and thinking. You may wish to share this score with your doctor to discuss whether you have had changes with your memory and thinking.

Based on the Montreal Cognitive Assessment Administration and Scoring Instructions (2010) available at: <http://www.mocatest.org>.

You should talk to your doctor if today's cognitive test score is less than normal or if you have questions about your cognitive test score. Your doctor will be able to answer your questions and decide whether more testing or treatments are right for you.

1.0 3.11.2020

Reach Out Cognition
Cognitive Screening
Date:

We did a cognitive test today as a part of the Reach Out Cognition Project. Your score on the Self-Administered **Gerocognitive** Exam (SAGE test) was: _____ out of 22.

What does your cognitive test score mean?

If your score was	Comment and Action
17 or above	Your Self-Administered Gerocognitive Exam (SAGE test) score today is within the normal range . You don't need to do anything right now.
15 and 16	Individuals with these scores are likely to have mild memory or thinking impairments. Further evaluation by a physician is recommended.
14 and below	Individuals with these scores are likely to have a more severe memory or thinking condition. Further evaluation by a physician is recommended.

Reference: Scharre DW, Chang S-I, Murden RA, Lamb J, Beversdorf DQ, Kataki M, Naharaj HN, Bornstein RA: Self-administered **Gerocognitive** Examination (SAGE): A brief cognitive assessment instrument for Mild Cognitive Impairment (MCI) and early dementia. *Alzheimer Dis Assoc Disord* 2010;24:64-71

Please note that SAGE screening is not a diagnostic test of any condition. You should talk to your doctor if today's cognitive test score is less than normal or if you have questions about your cognitive test score. Your doctor will be able to answer your questions and decide whether more testing or treatments are right for you.

Appendix T- Supplement: Instructions for taking your BP

DETAILED INSTRUCTIONS ON TAKING A BLOOD PRESSURE MEASUREMENT

Breathe normally and do not hold. When the correct pressure is reached, the inflation stops and the pressure gradually decreases. If the required pressure was not reached, the device will automatically inflate additional air into the cuff.

- Open the Cardio-App on your iPhone or Android device.
- Unscrew the cuff from around the CardioArm to switch on the device and pull the tie to open the cuff **loop**.
- Fit the CardioArm cuff around your upper arm. You can review the instructions for proper cuff placement at any point.
- Press the green **START** button on the Cardio App to start measuring. The cuff will inflate automatically. **Relax**, do not move and do not tense your arm muscle until the measurement result is displayed.
- The screen comprising of the systolic and the diastolic blood pressure and the pulse rate, is displayed on the Cardio-App.
- When the device has finished measuring, remove the cuff and wrap it around the CardioArm to switch off the device. If the cuff is left unattached, in a few moments the CardioArm switches off automatically. In this case, you will have to wrap the cuff around the CardioArm and re-open it to switch on the device.

BODY POSTURE DURING BLOOD PRESSURE MEASUREMENT

Note: Blood pressure can be affected by the position of the cuff and your **physical** condition.

Lying down during measurement:

- Be seated with your feet flat on the floor without crossing your **legs**.
- Straighten your arm alongside your body with your **elbow** facing up, front of you on a flat surface such as a desk or a table.
- The **middle** of the cuff should be at the same **level** as your heart.

Appendix U- Supplement: Instructions guide for tele-outcomes

Feature phone:

Version 1.0 4.10.2020

HUM00138470/ 1199877

Instructions for Outcomes

It is time for your x- month outcome! It will only take a few minutes. You will be mailed \$xx for completing the outcome. For assistance, questions, concerns or you would like a Reach Out Coordinating Team member to walk you through the outcome, feel free to call Reach Out at [contact].

What you need to do!

1 Step 1: Take your blood pressure using the app!	
1. Open the Qardio App on your iOS or Android phone.	
2. Ensure you are sitting as indicated in the BP Measurement instruction sheet.	
3. Take your blood pressure using your blood pressure cuff. Follow the instruction sheet for taking your BP. 
 a. Do this 3x so you are taking a total of 3x blood pressures, 1 minute a part! 	

Version 1.0 4.10.2020

HUM00138470/ 1199877

2 Step 2: Send us your blood pressures!

1. Open the Qardio App on your iOS or Android phone.

2. Click the HISTORY button on the bottom of your screen.

3. Select the upload icon in the upper right hand corner.

4. It will take you to a new screen where you can enter the study email address [contact].
 - a. Press send!

[figure not shown]
Version 1.0 4.10.2020

HUM00138470/ 1199877

3 Step 3: Complete survey link!

1. You will receive a link to complete a few questions. This could come in a text message or email.
 - a. If your phone has internet, you could click on the link, and complete the following questions.
 - b. If your phone does not have internet, you would copy and paste the link to your internet browser and complete the following questions.

You will receive a confirmation that your outcome was completed within 24 hours.

Thank you for completing your x-month outcome with Reach Out! You will receive your \$xx incentive within 10-20 business days. To confirm your address, call or text Reach Out at [contact].

If you have any trouble at all, call us! [contact]

Thank you!

[name]

Smart phone:

1 Step 1: Take a photo of yourself wearing the blood pressure cuff!

Version 1.0 4.10.2020 HUM00138470/ 1199877

Instructions for Outcomes

It is time for your x- month outcome! It will only take a few minutes. You will be mailed \$xx for completing the outcome. For assistance, questions, concerns or you would like a Reach Out Cognition Team member to walk you through the outcome, feel free to call Reach Out at [contact].

What you need to do!

1. Open your camera app.
2. Place the blood pressure cuff on the inside of your wrist.
3. Aim the camera towards your wrist with the cuff on it.
 - i. We only need to see your wrist and that the cuff is on your wrist. Please take the picture from above your elbow, the end of your fingers. We do NOT need to see your face.
4. When you're ready to take a photo, tape the shutter button located in the middle of the screen to take the photo.

2 Step 2: Send us that photo!

Version 1.0 4.10.2020 HUM00138470/ 1199877

1. Open your camera app.
2. Tap the picture you'd like to text.
3. Tap the share button on your screen. This looks different depending on the phone you are using.
 - i. If **iphone** it will be in the lower left corner
 - ii. If **android** it may be in the middle of the top of your screen.

4. Send your photo to [contact].

If you have any trouble at all, call us! [contact]

3 Step 3: Text us 3 different blood pressures (xxx/xxx)!

Version 1.0 4.10.2020 HUM00138470/ 1199877

Instructions for Taking Your Blood Pressure (BP) at Home

1. Take your blood pressure using your blood pressure cuff. Follow the instruction sheet for taking your BP.

2. Text your BP to [name] as XXX/ XXX.

3. Follow the instructions sheet for text messages.

- This is a text message and does not have to be a picture.

4. Do this 3x so you are sending us a total of 3 blood pressures to Reach Out!

4 Step 4: Complete survey link!

Version 1.0 4.10.2020 HUM00138470/ 1199877

1. You will receive a link to complete a few questions. This could come in a text message or email.
 - If your phone has internet, you could click on the link and complete the following questions.
 - If your phone does not have internet, you would copy and paste the link into your internet browser and complete the following questions.

Thank you for your interest in this study. Please complete the survey in your web browser by clicking the link below:
www.reachout-ed.com/edstudy/xxx/completeLink
This link is unique to you and should not be forwarded to others.

You will receive a confirmation that your outcome was completed within 24 hours.

Congratulations, you are all done!

Thank you for completing your x-month outcome with Reach Out! You will receive your \$xx incentive within 10-20 business days. To confirm your address, call or text Reach Out at [contact].

If you have any trouble at all, call us! [contact]

Thank you!
[name]
